13.3.1 Interim Analyses for Futility per cohort

For futility, the trial will be stopped early if $\Pr[\theta_s < 0.60 \mid \text{data}] > 0.90$, where θ_s denotes the proportion of patients who successfully receive surgery. That is, given the outcomes from the patients who have already been evaluated, if it is determined that there is a more than 90% chance that the surgery rate is 60% or less, the trial will be stopped for futility. Assuming a prior distribution of θ_s of $\sim \text{beta}(1.2, 0.8)$ for this experimental treatment against a constant 60%, pre-defined stopping boundaries corresponding to this probability criterion are provided in the following table. Once 3 patients have been enrolled in a cohort, follow the instructions in this table according to the schedule described above.

If there are this many (or more) patients whose surgery status is determined	Stop if there are this many or fewer patients who received surgery	If there are this many (or more) patients whose surgery status is determined	Stop if there are this many or fewer patients who received surgery
3	0	15*	6
5	1	17	7
7	2	19	8
9	3	20	9
11	4	22	10
13	5	24	11

* Cohorts B and C will stop at 15 patients regardless of the number of patients who received surgery

Three patients will be accrued first. If 0 of the 3 patients receive surgery in a given cohort as scheduled, the cohort should be stopped and the treatment will be declared as not feasible for this population. If there is at least 1 patient with surgery, the next patient will be entered in the study, unless the trial needs to stop according to the toxicity boundaries below. Check continuously as described above for sufficient surgery rate assuming the trial does not stop for toxicity first. The operating characteristics for futility and toxicity are summarized below the toxicity rules.

13.3.2 Interim Analyses for Toxicity

Under the same model described for futility, toxicities will be monitored assuming a prior probability of toxicity following $\text{Beta}(0.6, 1.4)$ in the current treatment arm against a constant rate of 0.30. Based on a previous study, we assume that a 15% rate of toxicity events would be acceptable and a 30% rate of toxicity would be unacceptable. [68] For trial monitoring and decisions about future trials, extreme toxicities (TOX) will be defined as any grade 3 or higher adverse event that is possibly, probably, or definitely related to any therapy received on this protocol and occur between the first dose of Durvalumab and surgery (or 4 weeks after that dose if the patient does not receive surgery as scheduled) with the following exception. Any grade 3 adverse event that is

potentially treatable with steroids will only count as an extreme toxicity if it does not improve to grade 2 or better within 2 weeks. Grade 3 nausea or vomiting that responds to anti-emetics within 72 hours and asymptomatic grade 3 or 4 lipase or amylase elevations will not count as TOX. The trial will be terminated if $\text{Prob}(\Theta_{\text{TOX}} > 0.30 | \text{data}) > 0.9$, where Θ_{TOX} is the proportion of patients experiencing a TOX event. Following this rule, the trial will be terminated according to the following table once the first 3 patients are evaluable.

If there are this many patients (or more) with TOX	3	4	5	6	7	8	9	10	11
Stop the cohort if there are this many (or fewer) patients who are evaluable (have TOX or completed 4 weeks after first Durvalumab dose without TOX)	3	7	9	12	14	17*	20	22	25*

* Always stop with 25 patients in Cohort A, but if 11 or more patients have TOX, then this treatment regimen is too toxic for further use. Always stop at 15 patients in Cohorts B and C, but if 8 or more patients have TOX, then this regimen is too toxic for further use.

Three patients in each cohort will be accrued first. If 3 of the 3 patients have TOX, stop that cohort and the treatment will be declared as too toxic for that cohort. If there is at least 1 patient with surgery without TOX, the next patient will be entered in the study, unless the trial needs to stop according to futility boundaries above. Check continuously as described above for toxicity assuming the trial does not stop for futility first. The operating characteristics for the combined futility and toxicity are summarized in the following table

The operating characteristics for the combined futility and toxicity based on Multc Lean are shown in the following table, assuming that toxicity and surgery rates are independent.

		Stop if $\text{Prob}(\Theta_{\text{TOX}} > 0.30 \text{data}) > 0.90$ or $\text{Prob}(\Theta_{\text{S}} < 0.60 \text{data}) > 0.90$					
		Cohort A (N=25)			Cohorts B and C (N=15)		
True Toxicity Rate	True Surgery Rate	Pr(stop early)	Mean Number of Patients	Median (25 th %ile, 75 th %ile)	Pr(stop early)	Mean Number of Patients	Median (25 th %ile, 75 th %ile)
0.10	0.50	0.59	16.2	19 (7, 25)	0.43	11.4	15 (7, 15)
0.20	0.50	0.62	15.6	17 (7, 25)	0.46	11.1	15 (7, 15)
0.30	0.50	0.69	13.9	12 (5, 25)	0.55	10.3	12 (5, 15)
0.40	0.50	0.83	11.2	7 (4, 19)	0.69	8.9	7 (4, 15)
0.50	0.50	0.94	8.3	6 (4, 11)	0.84	7.3	6 (4, 11)
0.10	0.60	0.27	20.8	25 (20, 25)	0.21	13.2	15 (15, 15)

0.20	0.60	0.32	20.0	25 (15, 25)	0.25	12.8	15 (15, 15)
0.30	0.60	0.46	17.6	25 (7, 25)	0.37	11.8	15 (7, 15)
0.40	0.60	0.69	13.7	11 (5, 25)	0.57	10.1	11 (5, 15)
0.50	0.60	0.90	9.6	7 (4, 12)	0.78	8.1	7 (4, 12)
0.10	0.70	0.09	23.5	25 (25, 25)	0.08	14.3	15 (15, 15)
0.20	0.70	0.14	22.5	25 (25, 25)	0.12	13.9	15 (15, 15)
0.30	0.70	0.31	19.8	25 (12, 25)	0.27	12.7	15 (12, 15)
0.40	0.70	0.61	15.2	15 (6, 25)	0.50	10.8	15 (6, 15)
0.50	0.70	0.87	10.4	7 (4, 16)	0.74	8.6	7 (4, 15)
0.10	0.80	0.02	24.6	25 (25, 25)	0.02	14.8	15 (15, 15)
0.20	0.80	0.08	23.6	25 (25, 25)	0.07	14.3	15 (15, 15)
0.30	0.80	0.27	20.6	25 (20, 25)	0.22	13.1	15 (15, 15)
0.40	0.80	0.59	15.8	17 (7, 25)	0.47	11.1	15 (7, 15)
0.50	0.80	0.86	10.7	7 (4, 16)	0.73	8.8	7 (4, 15)

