If, after appropriate workup, in the opinion of the investigator, the underlying diagnosis for the abnormality remains unexplained, or is considered attributable to investigational product, permanent discontinuation of dosing for the study subject should be considered. Each reported event of hepatic function abnormality will be followed by the investigator and evaluated by the supporting company. If the etiology of the event remains unconfirmed and/or is considered related to investigational product, a prompt cumulative review of safety data and the circumstances of the event in question will be conducted and assessed by the AstraZeneca safety review committee (or equivalent) to determine whether continued dosing of current study subjects and/or study entry should be interrupted, whether the protocol will be modified, or whether the study will be discontinued permanently. Review and approval by the AstraZeneca safety review committee (or equivalent) is required for resumption of subject dosing or study entry in the event that the study is interrupted. Where applicable, regulatory authorities IRBs/IECs will be notified of any actions taken with the study.

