13.3 Interim Monitoring

A Bayesian sequential monitoring design[66, 67] will be used to monitor the trial for surgery and toxicity rates. Generally, interim analyses will begin after 3 patients become evaluable, and will then be performed continuously to ensure that patients are exhibiting reasonable toxicity and surgery rates to continue the trial. Specific rules are in each subsection below. Since 1-2 patients are expected to be enrolled each month, monitoring data will be kept up-to-date and the tables below checked prior to consenting each patient once the 3rd patient in each cohort has been on study 4 weeks after the first dose of Durvalumab. Enrollment will not need to wait for the previous patient to become evaluable, but the rules will be checked for all evaluable patients before consenting each patient. This includes a risk of 1-2 patients entering on the study beyond the designed stopping rules, which is considered a reasonable risk. If accrual occurs faster than 1-2 patients per month, this practice will be reconsidered. All calculations for stopping boundaries and operating characteristics were performed in Multicenter Lean Desktop v2.1.

Patients will be evaluable once they have received the first dose of Durvalumab/tremelimumab, durvalumab/oleclumab or durvalumab/monalizumab and have then had 8 weeks time to go to surgery. If surgery has not occurred by 8 weeks then for monitoring these patients will have been considered not to have gone to surgery even if they do after 8 weeks. Patients will be allowed up to 12 weeks to complete surgical resection. If surgical resection is not done within 12 weeks from then patient will be removed from clinical trial

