13.3.3 Interim Analyses for Toxicity Post Surgery Immune-therapy

Under the same model described for futility and toxicity above, toxicities on immune-therapy after surgery will be monitored assuming an a priori probability of toxicity following Beta(0.4,1.6) in the current treatment against a constant rate of 0.20. For trial monitoring and decisions about future trials, extreme toxicities (TOXpost) will be defined as any grade 3 or higher adverse event that is possibly, probably, or definitely related to any therapy received on this protocol and occur after surgery between the first dose of adjuvant immune-therapy and the final dose received (up to 12 weeks) with the following exception. Any grade 3 adverse event that is potentially treatable with steroids will only count as an extreme toxicity if it does not improve to grade 2 or better within 2 weeks. Grade 3 nausea or vomiting that responds to anti-emetics within 72 hours and asymptomatic grade 3 or 4 lipase or amylase elevations will not count as TOXpost. The trial will be terminated if $\text{Prob}(\text{TOXpost} > 0.20 \mid \text{data}) > 0.9$. Following this rule, the trial will be terminated according to the following table once the first 3 patients are evaluable.

If there are this many patients (or more) with TOXpost	2	3	4	5	6	7	8
Stop the cohort if there are this many (or fewer) patients who are evaluable (have TOXpost or completed 4 weeks after first adjuvant immune-therapy dose without TOXpost)	3	6	9	13	17	21	25*

* Only patients who successfully have surgery and begin treatment with immune-therapy will be included. The table goes to 25 patients as the maximum of possible patients.

Three patients in each cohort will be accrued first. If 2 of the 3 patients have TOXpost, stop this portion of the trial and the adjuvant treatment will be declared as too toxic for this population. Check continuously as described above for toxicity. The operating characteristics (OCs) for this stopping rule for are summarized in the following table assuming all 25 or 15 patients in each cohort receive surgery and start adjuvant immune-therapy. Since we do not expect all 25 or 15 patients to enter this portion of the study, the OCs are slightly over-estimated.

		Stop if $\text{Prob}(\text{TOXpost} > 0.20 \mid \text{data}) > 0.90$					
		Cohort A (N=25)			Cohorts B and C (N=15)		

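### A treatment-related death counts as one ordinary toxicity event, with no trigger of its own for study entry, so the pre-operative rule lets a cohort continue after 2 related deaths in 3 or 4 patients or 3 in 5 or 6 if enough survivors reach surgery

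*Combined protocol and SAP*

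**What the plan says.** **Pre-operative rule (13.3.2).** The text reads: "extreme toxicities (TOX) will be defined as any grade 3 or higher adverse event that is possibly, probably, or definitely related to any therapy" given under the protocol. Steroid-treatable grade 3 events that improve within 2 weeks, briefly treated nausea or vomiting, and asymptomatic lipase or amylase rises are excluded. The event must "occur between the first dose of Durvalumab and surgery (or 4 weeks after that dose if the patient does not receive surgery as scheduled". The TOX rate has a Beta(0.6, 1.4) prior and is tested "in the current treatment arm against a constant rate of 0.30"; the cohort stops when the posterior probability of exceeding 0.30 is above 0.90. After the first three patients, one patient operated on without TOX is enough to enter the next, unless futility stops the cohort.

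**Post-surgery rule (13.3.3).** Here "extreme toxicities (TOXpost) will be defined as any grade 3 or higher adverse event" related to protocol therapy, counted between the first and final adjuvant doses (up to 12 weeks) and tested against 0.20 with a Beta(0.4, 1.6) prior.

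**Timing (13.3, 13.4).** In general, "interim analyses will begin after 3 patients become evaluable". The futility/toxicity summary to the IND Office Medical Affairs and Safety Group also starts after the first three evaluable patients per cohort, then follows every 2 to 4.

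**Deaths (7.5, 7.6.1.2).** An unexpected, related fatal event needs a written report to the IND Office within 24 hours; other SAEs have 5 working days. A death not clearly due to progression goes to the supporting company within 24 hours. Neither section mentions enrolment.

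**Liver abnormality (7.6.2).** A Hy's law case of unconfirmed cause, or considered drug-related, prompts a cumulative safety review "to determine whether continued dosing of current study subjects and/or study entry should be interrupted". No minimum number of patients applies, and resuming after an interruption needs that committee's approval.

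**The concern.** TOX and TOXpost are binary, so grades 3, 4 and 5 carry equal weight. The 30% and 20% reference rates were set for grade 3 or higher toxicity in general, and the plan has no separate limit or action for death. A rule calibrated to tolerate a moderate rate of severe but recoverable events will react slowly to deaths.

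The patients are candidates for potentially curative resection, and Cohorts B and C bring combinations newly added to this pre-operative protocol. The plan accepts elsewhere that a single event can call for a review of study entry, but it does this for a liver abnormality and not for a drug-related death. Staff who follow section 13.3.2 literally would enter the next patient after early related deaths, because the text tells them when to do so.

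**Working it through.** **Inputs.** Priors, reference rates, the 0.90 threshold and the boundary tables come from 13.3.1 to 13.3.3; cohort sizes of 25 (A) and 15 (B, C) come from 13.2.

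**Formulas**, for x events or s surgeries in n patients:
- Pre-operative toxicity: P = 1 − BetaCDF(0.30; 0.6 + x, 1.4 + n − x); stop if P > 0.90.
- Futility: P = BetaCDF(0.60; 1.2 + s, 0.8 + n − s); stop if P > 0.90.
- Post-surgery toxicity: P = 1 − BetaCDF(0.20; 0.4 + x, 1.6 + n − x); stop if P > 0.90.

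**Step 1: reproduce the plan's tables.** All futility and post-surgery boundaries reproduce. So do eight of the nine pre-operative boundaries (4/7 gives 0.901, 5/9 gives 0.922, and so on to 11/25 at 0.918). The exception is the first: the criterion also stops at 3/4 (0.935), while the table prints 3/3. The printed operating characteristics match 3/4. That entry needs reconciling, and 3 of 4 is not used below.

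**Step 2: related deaths under the pre-operative rule.** A pre-operative death is also a non-surgery. If every survivor is operated on without TOX:

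| Deaths / evaluable | P(TOX rate > 0.30) | Surgeries | P(surgery rate < 0.60) | Stop? |
|---|---|---|---|---|
| 2/3 | 0.838 | 1/3 | 0.765 | No |
| 2/4 | 0.734 | 2/4 | 0.618 | No |
| 3/5 | 0.875 | 2/5 | 0.776 | No |
| 3/6 | 0.800 | 3/6 | 0.657 | No |

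The printed table also gives no stop in these four states.

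**Step 3: the condition on survivors.** Futility stops at 0/3 (0.958), 0/4 (0.983), 1/5 (0.942) and 1/6 (0.973), but not at 1/4 (0.881) or 2/6 (0.875). So 2 deaths in 3 continues only if the third patient is operated on. The requirement is one of the two survivors at 2 in 4, both survivors at 3 in 5, and two of the three at 3 in 6.

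**Step 4: before the first look.** Two related deaths in the first two patients give 0.928, above the plan's own threshold, but no check is scheduled at n = 2.

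**Step 5: post-surgery rule.** 2/3 gives 0.907, 3/5 gives 0.948 and 3/6 gives 0.914, and all stop. 2/4 gives 0.846 and continues.

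**Step 6: windows.** TOX ends at surgery, or at 4 weeks if there is no surgery as scheduled. TOXpost starts at the first adjuvant dose, 4 to 12 weeks after resection (5.1), and ends at the final dose. A related death between surgery and the first adjuvant dose counts in neither. Nor does one after the final dose, although SAEs are collected for 90 days (7.4.1).

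**Step 7: illustration.** Assume a 10% related pre-operative death rate with no other TOX; this figure is not from the documents. The table in 13.3.2 assumes toxicity and surgery are independent, so deaths were modelled jointly as non-surgeries, with looks at every n from 3.
- 80% of survivors operated on (0.9 × 0.80 = 72% overall): Pr(stop early) is 0.056 for N = 15 and 0.062 for N = 25.
- 89% of survivors operated on (80% overall): 0.02 for both. The plan's table also prints 0.02 at toxicity 0.10 and surgery 0.80.

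The chance of at least one such death is 1 − 0.9^15 = 0.79 in 15 patients and 1 − 0.9^25 = 0.93 in 25.

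**The case against.** The strongest reply is that the boundaries are not the only safeguard. The IND Office must review and approve the summaries, unexpected related deaths reach it within 24 hours, SAEs go to the IRB and FDA, and the sponsor may close the study. A reader might infer that the plan obliges everyone to keep enrolling through deaths, or that it accepts a 30% death rate. The documents support neither: any of these bodies could act, and 30% and 20% are never presented as limits for death. What remains is that none of these routes states a trigger for study entry.

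Pooling grade 3 and higher events is also a deliberate choice with published operating characteristics, and the exclusions remove some minor laboratory events. That is a fair defence of the boundaries, which need not change. The contrast with 7.6.2 is an asymmetry, not a flat contradiction.

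A reader might also infer that both rules are equally permissive, or that the drugs are known to be lethal in this setting. The post-surgery rule already stops at 2 of 3 and 3 of 6. Section 2.4.3.3 reports no treatment-related death in the monalizumab hematology/oncology trials, and section 2.5.4 reports that none of the six deaths on oleclumab plus durvalumab was treatment-related. Section 2.6 says toxicity kept none of the 14 Cohort A patients who reached the point of resection from surgery. The 10% rate is only an assumption, and even at that rate the early states are uncommon: 2 or more deaths in 3 patients has probability 0.028, and 2 or more in 4 has 0.052.

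Finally, 13.2 expects Cohort A to be about fully enrolled when the revision is approved, so its pre-operative figures have little prospective force.

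**Conclusion.** The concern holds as a gap in the monitoring plan. A related death has no weight or trigger beyond one count, no statistical check or routine summary precedes the third evaluable patient, and one interval after surgery is covered by neither rule. Under the pre-operative rule a cohort continues at 2/3, 2/4, 3/5 and 3/6 related deaths (posteriors 0.734 to 0.875), conditional on the surgeries in step 3. Under the post-surgery rule only 2/4 among these states continues.

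The counts and posteriors rest on the plan's own priors and thresholds. The early-stopping probability of about 0.02 to 0.06 rests on the assumed 10% death rate and the assumed surgery rates. The point matters mainly for Cohorts B and C. It is worth correcting before further enrolment, but it does not show that the boundaries are miscalculated for grade 3 or higher toxicity overall.

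**What to change.** Reconcile 13.3.2 and 13.3.3 with 7.6.2 by adding one sentence to each. From the first patient, and independently of the tables, any grade 5 event at least possibly related to study therapy, whenever it occurs on study, holds new consent and enrolment to that cohort until the IND Office Medical Affairs and Safety Group has reviewed it and documented a decision. This goes one step beyond 7.6.2, which triggers a review but not an automatic hold. At a minimum, the plan should state what happens to study entry after such a death.

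Align 7.5 so that every related death, expected or not, reaches that group promptly. The present 24-hour duty to the IND Office covers only unexpected related events, and the 24-hour report in 7.6.1.2 goes to the supporting company.

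Leave the Bayesian boundaries, the doses and the treatment rules for enrolled patients unchanged.

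The cost is a sentence in each of the two monitoring sections, a small edit to the reporting text, and an occasional short enrolment pause for a death later judged unrelated. The reviewing group already exists.

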Lung or liver resection will be scheduled approximately 3-weeks after the infusion of the immunotherapeutic agents. Completing up to 4 months of chemotherapy after surgical resection instead of immunotherapy (durvalumab for cohort A, durvalumab/oleclumab for cohort B, or durvalumab/monalizumab for cohort C) continuation is an option depending on the preferences of the treating physician/patient (i.e., subjects can opt out of the planned post-operatively immunotherapy). Post-operative therapy will be either chemotherapy per physician/patient choice or 4months of immunotherapy. As synchronous primary lesions are allowed in this study, the appropriate clinical care as determined by the treating multidisciplinary team for addressing the primary lesion will be allowed. Though primary resection on clinical trial prior to liver resection will not be allowed, primary resection may be simultaneous with liver resection or occur after liver resection. In addition as short course radiation therapy (5 days) is often employed for rectal primaries this will be allowed in this clinical trial as long as radiation therapy is \geq 1 week from first dose of study treatment. Factoring the occurrence of potential immune mediated AEs prior to resection, an allowance of a 3-10 weeks from neoadjuvant therapy administration will be permitted to complete metastatic and/or primary resection

As the mechanism of action of immunotherapy should not impact wound healing, patients may start adjuvant therapy as early as 4 weeks after resection, per treating physician discretion, provided they have achieved adequate status after surgery (ex. Resolution of post-operative concerns). Post-operative therapy thus can begin between 4weeks to 12 weeks post-operatively. However, if patients require >12 weeks for postoperative recovery they will not be allowed to initiate adjuvant immunotherapy.

The study design schematic is below.

Study Schematic

5.1.1 Screening visit.

If a patient is thought to be a potential candidate for the trial, then he/she can be offered participation and, if agreeable, will undergo screening procedure outlined below from D-14 to D-1. Previously conducted HIV, PT/PTT, and hepatitis testing within 30 days does not need to be repeated and will be acceptable for screening purposes (tests performed at outside laboratories as standard of care testing will be accepted).

Table 5.1-1: Screening Procedural Outline

Procedure	Screening Visit From D-14 to D-1	Notes

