10. STUDY CALENDAR AND SCHEDULES

Table 10.1 Study Calendar from Enrollment until Surgical Resection

TIME PERIOD	Screening	Wk	Wk	Comment
		1	4**	
	within 14 days	+/-3d	3 - 10 weeks**	
PROCEDURE				
Cohort A: Tremelimumab + Durvalumab		X		
Cohort B: Durvalumab + Oleclumab		X		
Cohort C: Durvalumab + Monalizumab		X		
Liver/lung resection			X	
Clinic Visit	X	X	X	
Physical Examination	X	X	X	
Vital Signs	X	X	X	Including BP, HR, temperature. Obtain vital signs
Review of Concomitant Medication	X	X	X	
Laboratory	X	X	X	CBC w/differential and platelet count, LFTs (ALT, AST, total bilirubin, alkaline phosphatase), BUN or serum urea level, creatinine, Ca, Mg, Na, K, Cl, glucose)
CEA lab		X	X	
HIV and hepatitis and PT/PTT	X (within 30 days allowed)			HIV, hepatitis B and C testing and PT/PTT
Specialized laboratory tests	X		X	Lipase, amylase, TSH, FT4
Pregnancy test (WOCBP only)	X	X		Serum or urine pregnancy test to be done within 72 hours prior to first dose.
ECOG PS	X	X	X	see appendix 1
Adverse Events Assessment	X		X	Per CTCAE v4.03 for Cohort A and v5.0 for Cohorts B and C
CT C/A/P with IV contrast with tumor measurements	X (within 30 days)		X	
Immunogenicity Assessment (special lab)		X	X	
Liver biopsy (tumor)	X			
Immuno- genicity Assessments, Peripheral Blood		12 red top tubes of blood with 5ml each will be collected for immunological assessment. See section 5.1.3 (up to 4 missed blood draws are allowed)		
**Factoring the occurrence of potential immune mediated adverse events prior to resection, an allowance of 3 - 10 weeks after the administration of neoadjuvant therapy will be permitted to complete metastatic and/or primary resection.				

CEA: Carcinoembryonic Antigen; ECOG PS: Eastern Cooperative Oncology Group Performance Status; TSH: Thyroid stimulating hormone; FT4: Free T4; WOCBP: Women of child bearing potential; CT C/A/P: CT scan chest, abdomen and pelvis

Table 10.2 Post-Resection Study Calender for Cohort A (Durvalumab + Tremelimumab)

(Week 1 begins the day Durvalumab treatment is given)

TIME PERIOD	Post-operative evaluation	Wk	Wk	Wk	Wk	Wk	Comment
		1	5	9	13	every 4months	
	(0.5-2wks post surgery)	+/-3d	+/-7d	+/-7d	+/-7d	+/-6 weeks	
PROCEDURE							
Durvalumab		X	X	X	X		If patient requires >12 weeks for postop recovery, they will not be initiated on adjuvant immunotherapy
Clinic Visit	X	X	X	X	X	X	
Physical Examination	X	X	X	X	X	X	
Vital Signs	X	X	X	X	X	X	Including BP, HR, temperature
Review of Concomitant Medication	X	X	X	X	X		

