13.4 Analysis Plan

Primary endpoint: Each combination regimen will be considered feasible if at least 80% of patients successfully undergo surgery. It will be infeasible if fewer than 60% of patients can undergo surgery. If the successful surgery rate is between 60% and 80%, then consideration will be given to toxicity, clinical outcome measures, and immune changes to determine whether this regimen warrants further investigation. The 95% posterior credible interval will be calculated for proportion of patients undergoing surgery. Adverse events will be tabulated.

Additional analyses: Demographic and patient baseline disease characteristics will be summarized for all patients. Descriptive tables and figures will be presented for immune markers. Overall (OS) and relapse-free survival (RFS) will be calculated and plotted by Kaplan-Meier methods[69]. Relationships between baseline characteristics, immune markers, and outcomes (response, OS, or RFS) will be explored with logistic or Cox[70] models as patient numbers allow. No formal hypotheses will be tested, but results will be used to design the next formal trial if toxicity and feasibility are reasonable for further investigation.

The Investigator is responsible for completing a futility/toxicity summary report, and submitting it to the IND Office Medical Affairs and Safety Group, for review and approval. This should be submitted after the first 3 evaluable patients per cohort, have surgery or 4 weeks after the first dose of immune-therapy, whichever comes first, and

every 2 to 4 evaluable patients thereafter, according to the schedule described in the toxicity/futility monitoring tables.

On every summary submission, futility information about previous reported patients will need to be updated to week eight.

A copy of the cohort summary should be placed in the Investigator's Regulatory Binder under "sponsor correspondence".

REFERENCES

1. Siegel, R., et al., *Cancer statistics, 2014*. CA Cancer J Clin, 2014. **64**(1): p. 9-29.
2. Scheele, J., et al., *Resection of colorectal liver metastases*. World J Surg, 1995. **19**(1): p. 59-71.
3. Adam, R. and E. Vinet, *Regional treatment of metastasis: surgery of colorectal liver metastases*. Ann Oncol, 2004. **15 Suppl 4**: p. iv103-6.
4. Parkin, D.M., et al., *Global cancer statistics, 2002*. CA Cancer J Clin, 2005. **55**(2): p. 74-108.

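### Pre-surgery TOX counting ends at week 4 for patients who never reach surgery, so a later related grade 3+ event that prevents resection is left out of the TOX rule and the final toxicity call

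*Combined protocol and SAP*

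**What the plan says.** Section 13.3.2 defines TOX for monitoring and for decisions about later trials. It covers related grade 3 or higher events, with stated exceptions, that "occur between the first dose of Durvalumab and surgery (or 4 weeks after that dose if the patient does not receive surgery as scheduled". In the stopping table a patient is "evaluable (have TOX or completed 4 weeks after first Durvalumab dose without TOX". The same count gives the final call: 11 or more of 25 in Cohort A, or 8 or more of 15 in Cohorts B and C.

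*As scheduled* is not defined. It also appears in Section 13.3.1 ("If 0 of the 3 patients receive surgery in a given cohort as scheduled"). The candidates for its meaning are:

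- **About 3 weeks:** when Section 5.1 says resection will be scheduled.
- **10 weeks:** Section 5.1, "Factoring the occurrence of potential immune mediated AEs prior to resection, an allowance of a 3-10 weeks from neoadjuvant therapy administration will be permitted"; the footnote to Table 10.1 agrees, "an allowance of 3 - 10 weeks after the administration of neoadjuvant therapy will be permitted to complete metastatic and/or primary resection".
- **8 weeks:** Section 13.3, "If surgery has not occurred by 8 weeks then for monitoring these patients will have been considered not to have gone to surgery".
- **12 weeks:** Section 13.3, "Patients will be allowed up to 12 weeks to complete surgical resection".

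Section 13.4 requires earlier patients to be updated, but for futility only: "On every summary submission, futility information about previous reported patients will need to be updated to week eight". The post-surgery measure (TOXpost, Section 13.3.3) starts at the first adjuvant dose.

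**The concern.** The window closes early for the patients in whom late toxicity has done most harm to the plan. On the 8-, 10- or 12-week reading, an event at week 6 counts if the patient recovers and is resected at week 7. The same event does not count if it keeps the patient from surgery altogether. Section 5.1 grants the longer window because immune-mediated events may delay resection, so delay is foreseen.

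TOX drives both early stopping and the statement that a regimen is too toxic for further use. If qualifying toxicity appears late and blocks surgery, both rest on a count that omits it. The operating characteristics in Section 13.3.2 assume that toxicity and surgery are independent, so they cannot show the effect.

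**Working it through.** **1. Which patients are capped.** Take a qualifying event at week 6.

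| Meaning of *as scheduled* | Never resected | Resected at week 7 |
|---|---|---|
| about 3 weeks | not counted | not counted |
| 8, 10 or 12 weeks | not counted | counted |

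The first column does not depend on the reading. TOXpost cannot recover the event, because a patient who is not resected has no adjuvant dose. The week-eight update names futility information only.

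**2. Reproducing the plan's figures.** Inputs from Sections 13.3.1 and 13.3.2: TOX prior Beta(0.6, 1.4) against 0.30; surgery prior Beta(1.2, 0.8) against 0.60; cutoff 0.90; checks from patient 3; N = 25 or 15. With x TOX and s surgeries in n patients, stop if

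- Pr(θ > 0.30) > 0.90, where θ ~ Beta(0.6 + x, 1.4 + n − x), or
- Pr(θ < 0.60) > 0.90, where θ ~ Beta(1.2 + s, 0.8 + n − s).

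An exact calculation over (n, x, s), counting stops up to patient N − 1, gives 0.585 (N = 25) and 0.470 (N = 15) at toxicity 0.40 and surgery 0.80. The plan prints 0.59 and 0.47. All 40 printed early-stopping probabilities reproduce to within 0.005. The final limits also agree with the criterion: the posterior probability is 0.918 at 11 of 25 and 0.960 at 8 of 15, against 0.893 at 7 of 15.

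**3. Adding late events that block surgery.** Let t be the true rate of qualifying events before surgery over the full window, and f the share that occur after week 4 and prevent surgery. The documents give no value for f, so it is an assumption. Each patient is one of:

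- late and blocked, probability t·f: no surgery; TOX not counted (as written) or counted;
- TOX in the window, probability t(1 − f): surgery with probability 0.80;
- no TOX, probability 1 − t: surgery with probability 0.80.

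Pr(stop early), both rules together, as written → late events counted:

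| t | N | f = 2% | f = 10% | f = 25% |
|---|---|---|---|---|
| 0.30 | 25 | 0.252 → 0.267 | 0.200 → 0.271 | 0.136 → 0.281 |
| 0.30 | 15 | 0.212 → 0.224 | 0.173 → 0.228 | 0.123 → 0.237 |
| 0.40 | 25 | 0.560 → 0.586 | 0.459 → 0.588 | 0.304 → 0.595 |
| 0.40 | 15 | 0.449 → 0.471 | 0.372 → 0.474 | 0.257 → 0.481 |

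The loss is 0.012 to 0.026 at f = 2%, 0.055 to 0.129 at 10%, and 0.114 to 0.291 at 25%. The as-written figures already count each blocked patient as a non-surgery, so the futility rule does not make up the difference.

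These figures use the stated posterior criterion, which also stops at 3 TOX in 4 patients (posterior 0.935). The printed table stops only at 3 of 3. For the 10% and 25% shares, using it lowers each value by 0.010 to 0.015 and leaves the comparison unchanged.

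**4. Cost where toxicity is acceptable.** At t = 0.15, for f = 10% and 25%: N = 25, 0.035 and 0.035 as written against 0.042 and 0.048 counted; N = 15, 0.034 and 0.034 against 0.040 and 0.046. The rise is about 0.006 to 0.013.

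**5. What the trial has seen.** Section 2.6 reports that toxicity kept none of 14 Cohort A patients from surgery. The one-sided 95% upper limit is 1 − 0.05^(1/14) = 0.193.

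**The case against.** **The scenario needs a prior delay.** Surgery is planned at about week 3. An event that starts before then and cancels surgery falls inside the window and counts. Only patients already delayed past week 4 can contribute. At t = 0.40 and f = 25%, late blocked patients are 0.40 × 0.25 = 10% of the cohort. If 20% of patients slipped past week 4 (an assumption), half of them would need such an event. This stands: the 10% and 25% shares have no basis in the documents, and the 2% column may be nearer the truth.

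**The event is not lost to safety oversight.** A reader might infer that late events go unseen, or that a regimen with 80% or more surgery is advanced with no look at toxicity. The documents do not support either inference. The event still reaches serious adverse event reporting where it is serious, the adverse event tabulation, and the surgery count as a non-surgery. Hy's-law hepatic events that are drug-related or unexplained trigger a cumulative safety review that can halt dosing or entry (Section 7.6.2). Section 13.4 weighs toxicity when 60% to 80% have surgery. It also makes use of the results for the next trial depend on toxicity being reasonable, whatever the surgery rate. These points stand, but none of them changes the TOX count.

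**The cap may be deliberate.** It matches the 4-week evaluability rule and gives unresected patients time at risk close to that of patients resected at about 3 weeks. That is a coherent choice, but the plan does not state it. On the longer readings it is not applied evenly, since a patient resected at week 8 is counted for 8 weeks.

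**Conclusion.** The gap in the definition holds on every reading for patients who are never resected. On the 3-week reading it extends to patients resected late. Its size is unknown: it may be nil in Cohort A, where none of 14 patients was kept from surgery by toxicity, and Cohorts B and C use other combinations. The table is a sensitivity range. It assumes surgery at 0.80 otherwise and that every late event blocks surgery. The larger losses should not be read as estimates for this trial. Minor to moderate: a prespecified count can understate toxicity, other safeguards are only partial or qualitative, and the repair is cheap.

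**What to change.** 1. The sponsor should reconcile the surgery times and limits in Sections 5.1 and 13.3 and Table 10.1, then define *as scheduled* in Sections 13.3.1 and 13.3.2 from the result. This review does not say which limit is right.
2. Count TOX from first dose to surgery or, without surgery, to the end of the reconciled window.
3. Keep entry into the interim counts at 4 weeks, but update each patient's TOX status at every later check and before the final call, as Section 13.4 already does for futility.
4. If the 4-week cap is intended, state the reason and report the full-window count beside it at each check and at the final call.

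**Cost.** Priors, limits and boundary tables stay. TOX status becomes final some weeks later. Unresected patients have a longer time at risk: 8 to 12 weeks is two to three times the present 4. At 15% toxicity, early stopping rises by about 0.006 to 0.013 for late shares of 10% to 25%.

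**Data.** Section 7.4.1 records serious events for 90 days (90/7 = 12.9 weeks) after the last durvalumab dose. That covers week 12 for a patient never resected, unless other anticancer therapy starts first and ends the reporting period (Section 7.5.1). The period for other adverse events is worded around the post-operative dose, so collection of non-serious grade 3+ events in unresected patients should be confirmed.
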